#### ***Partial breast re-irradiation by brachytherapy***

To re-irradiate, interstitial brachytherapy was the first and most commonly applied technique, using low (29,30,48,49,51), pulsed (30,52), or high dose rates (53). Vectors were implanted intra- or post-operatively, and the median delivered dose was about 46 Gy (ranging from 30 to 50 Gy).

Most of the published data come from single institution studies and are either retrospective (48,51,53) or prospective (29,54). The rate of 5-year second local relapse is about 10% (ranging from 0 to 26%) and the 5-year DFS rate about 60% (ranging from 31 to 85%). The rate of late complications is considered acceptable, with a Grade 3-4 complications rate around 8% (ranging from 3 to 11%). Fat necrosis is observed in about 20% of patients. Finally, cosmetic results are reported as good to excellent for 70% of women (ranging from 53% to 100%) but should be considered cautiously for retrospective studies.

#### ***Partial breast re-irradiation by external 3D-Conformal technique***

The main publication about adjuvant external radiotherapy for local relapse is a single institution retrospective study published in 2002 by the University of Pittsburgh using an external electron beam for a total dose of 50 Gy with conventional 2 Gy daily fractionation (27). With a median follow-up of 52 months, they experienced 20% of in-breast relapse despite 15% of positive margins.

The American Society of Radiation Oncology (RTOG) has just conducted a Phase II trial (RTOG 1014) (55), investigating, as primary endpoint, the tolerance (i.e. Grade 3 side effects as breast pain and skin fibrosis within 1 year) of 3D conformal PBI. The clinical target volume was defined as the post-operative cavity on CT scanner with an additive 25 mm margin submitted to twice-daily fractions of 1.5 Gy for a total dose of 45 Gy. With a planned quality assurance program, the investigators expected a Grade 3 toxicity rate as low as the one observed in the RTOG 0319 trial (evaluating the PBI in adjuvant irradiation for primary surgery, i.e. 4%). This trial, conducted in a large number of centers across the United States, recruited the expected 61 patients, and has just closed in June 2013.

## **2- Intra-operative radiation therapy (IORT)**

The IORT was developed to allow a dose escalation in tumors known as being highly radio-resistant or in deep local recurrences occurring in previously irradiated areas such as pelvic

cancers. This dose escalation was rendered possible by saving the surrounding healthy tissue during the surgery procedure and IORT (Electrons or 50kV photons) (56).

Then, IORT was delivered by linac-accelerators located in the surgical rooms requiring dedicated equipment but only developed in some specific centers such as Milan, Salzburg, Montpellier and Madrid in Europe.

Its use in breast cancer started in the early eighties but was, however, of limited use.

The recent development of different small and mobile accelerators (Mobetrons™, Eliott™ for mobile electrons and IntraBeam™ for mobile 50 kV x-rays) partly explained the increased interest and the recent large development of this technique. Due to their different radiobiological behavior, a comparison between these energies is not approvable (57) or must be read cautiously (58). Intrabeam™ is indeed known for presenting a very low-dose penetration (56,59). At a depth of 1 cm, the estimated delivered dose is only 5 to 7 Gy, which is substantially lower than the electron technique (60). Nevertheless, biological equivalence is difficult to determine precisely (58) whereas physical and biological aspects have not been proved to have significant consequences on local control.

Thanks to the recent development of this technique, ten clinical trials are open worldwide to evaluate IORT for breast cancer in adjuvant indications, but none in local relapses.

## 2.1. **Advantages of IORT:**

IORT has the advantage of a huge normal tissue sparing (61,62) and an excellent tumor delineation under visual control. This advantage allows minimizing potential geographical misses related to post-operative modifications generated by a delayed external irradiation.

IORT is described to have very low acute and late toxicity (45,63–68). Low-kilovoltage irradiation gives low side effects thanks to the spherical shape of the applicator, which avoids mobilizing the mammary gland in the post-lumpectomy cavity.

The spherical applicator allows therefore to irradiate the entire cavity very simply, thereby providing a low rate of fat necrosis (67,68) and good cosmetic outcome (67,69).

Moreover, the costs of these single fraction treatments seem lower than any other technique used for adjuvant radiotherapy; the saving represented by this new alternative is currently evaluated in a medico-economic randomized prospective trial conducted in France and supported by the National Institute for Cancer, INCa (70).

A consistent advantage of the technique is its unique attractive aspect of a one-day treatment. With both surgery and irradiation delivered during a one shot-procedure, IORT is a very simple treatment with maximal compliance and high benefits for quality of life.

## 2.2. Results of IORT:

The IORT experience in breast cancer started first in Montpellier in 1989 (62,64,71) and evaluated the role of a 10-Gy boost (delivered with electrons) associated with an additional 50-Gy post-operative whole breast radiation therapy (WBRT) (63,64). In this setting, very recent and mature results have been published in 2013, in a large multi-institutional ISIORT pooled analysis (63) with a cohort of 1100 patients and median follow-up of 72 months. The authors showed that a boost using IORT allowed an impressive local control rate of 99.2%.

IORT has been, more recently, evaluated in PBI setting for selected patients with a 20-21 Gy single dose:

A huge international Phase III trial, TARGIT A (45), including 2232 patients (pre-pathology arm) compared a single 20-Gy dose – delivered at the surface of the excision cavity - to a standard adjuvant whole breast radiotherapy. With a 4-year median follow-up (reached for only 20% of patients) the trial demonstrated the non-inferiority of the PBI approach to the traditional adjuvant WBRT. Fourteen percent of patients with definitive unfavourable histopathological prognostic factors received after PBI an additional external WBRT. Mature results are needed to reinforce the safety of this interesting approach.

The same trial was conducted with electrons in a large Italian Phase III trial for which mature results are still awaited.

In Montpellier, we published the results of a Phase II trial in highly selected patients with good prognosis tumors (older than 65, with ER-positive status, T1N0 unifocal non-lobular carcinoma resected with clear margins). The final results demonstrated the feasibility of this technique with very low acute and late toxicity and very good cosmetic results (65,72).

An international trial - Targit E (73) – has recently opened to evaluate the feasibility and results of this IORT in the elderly.

## 2.3. IORT for local relapse:

The only published study evaluating IORT for local relapse is a retrospective single-institution study conducted during 54 months and including 17 patients treated by heterogeneous treatments (50). Conducted in Mannheim, the results were published with a follow-up of 26 months and described no local relapse. A prospective multi-institutional trial is not yet available and is proposed in the current project.

## 3-Ancillary studies

### 3.1. Intrinsic hypersensitivity: Proteomic assay

Individuals vary widely in the susceptibility of the tissue to ionizing radiation damage. Current knowledge of individual variation is fragmentary; there is a need to monitor such adverse events and to predict their occurrence.

In this setting, our laboratory has developed in recent years a predictive assay based on flow cytometric assessment of radiation-induced T-lymphocyte apoptosis (RILA). This assay showed that no severe late effect was observed in patients with a high RILA level, with an excellent negative predictive value (NPV=99%). On the contrary, all patients with a severe toxicity had a low value of RILA but the positive predictive value of the test was low (PPV=20%) (74,75).

Based on these results and in order to improve the positive predictive value of the radiation induced late effect assay, we developed a quantitative proteomic approach to identify predictive radiobiological markers in patients with severe toxicity. First, we selected four patients with a low RILA value from the prospective studies mentioned above. Two patients had no toxicity at least four years after the end of treatment whereas two others patients developed a severe toxicity greater than Grade 2. T-lymphocytes have been isolated from whole blood and half of them have been irradiated ex-vivo. We then performed a quantitative proteomics workflow using an 8-plex iTRAQ labeling and after several fractionations to optimize resolution of analysis (off gel fractionation followed by nanoliquid chromatography), proteins were identified by tandem mass spectrometry (4800 plus MALDI TOF/TOF). More than 1300 total proteins were identified with high confidence (95%, one unique peptide). Among them, 5 proteins involved in several mechanisms including metabolism and energy production, apoptosis, calcium binding protein, and DNA damage repair are overexpressed and seem to be related with hypersensitive patients to RT (ongoing patent application). Biological predictive factors are warranted to identify the individual risk of development of severe late toxicity. As RILA has a low PPV, we propose here to prospectively identify patients with an intrinsic radiosensitivity through a protein assay. For that, blood samples (14 ml heparinized whole blood) will be performed before RT for each patient and the expression of five proteins will be assessed. This test will be mandatory in the RE-IORT 01 trial to validate our preliminary results of protein expression level in patients presenting with radiation-induced late effects and particularly of the positive predictive value of this test.

### 3.2. Genomics assay

Advances in molecular techniques have improved discovery of biomarkers associated with radiation exposure. A challenge still resides in characterizing signalling pathways involved in

molecular and cellular responses to radiological interactions in various biological fluids and tissues under different types of irradiation conditions (76). One of our collaborators (UA) is developing the devices, biomarkers and bioassays for the accurate determination of an individual's absorbed dose of ionizing radiation. The team has identified molecules in the bloodstream that could gauge the risk to predict the radiation level across species, from mice, non-human primates and human TBI patients, and for dose ranging from 0.1 to over 10 Gy and long periods post-exposure. These sets of samples show accurate dose predictions within 10 cGy by using a 30-genes CLPA detection panel on whole blood specimen with volumes less than 30 µl.

The team proposes to investigate a new set of biomarkers present among the miRNA in the pleural effusion and implement a test using a new assay chemistry or chemical ligation dependent probe amplification (CLPA) that uses a multiplex ligation assay with PCR amplification, and on chip capillary electrophoresis readout (CE). The CLPA has the tremendous advantage of being able to perform directly without the need of extracting the RNA, which simplifies the workflow and reduces noises introduced. In addition, the CLPA is a very fast assay (< 2 hour) in comparison to other commercially available kits (e.g qNPA, PCR (> 2-3 days) and very sensitive. The CLPA method is easily adapted to a variety of high-throughput platforms suitable for medical countermeasures, including generic planar microarrays, liquid bead arrays (e.g. the Luminex Map) or capillary electrophoresis systems

miRNAs are post-transcriptional regulators that bind to complementary sequences in the three prime untranslated (3'UTRs) regions of target mRNA, usually resulting in gene silencing. Nearly all miRNAs are conserved in closely related species and many have homologs in distant species. Other advantage in using miRNAs is the fact that many miRNAs are tissue specific and stable. Discovered just over a decade ago, miRNA is now recognized as one of the major regulatory gene families in eukaryotic cells. Through the profiling, miRNA expression has been identified as differentiation biomarkers, as well as cancer biomarkers. Recently, plasma miRNA have been identified as biomarkers for radiation exposure dosimetry. Several studies showed that miRNAs play important roles in cell signalling pathways, physiological processes, and human pathologies; and is believed to regulate more than 50% of the human genome by translational repression or target degradation and gene silencing. A few laboratories have applied complex genomic microarray techniques to investigate how miRNA expression profile may change in response to ionizing radiation. Most of these studies have examined changes in miRNA expression profiles in response to ionizing radiation in both murine and human cells and tissues. One group also examined miRNA in peripheral blood cells of radiotherapy patients which is so far the only characterization of miRNA expression signature in humans irradiated *in vivo* (77).

We propose to identify the miRNA present in the serum of the resected cavity of the patients and investigate how miRNA expression profiles may change in response to ionizing radiation in these samples. The technology platforms will provide new tools to evaluate radiation

toxicity during the course of therapy, based on an individual's biology, identifying people at risk for radiation illnesses.

**Finally, we propose a prospective and multicentre phase II trial to evaluate a new alternative approach combining a second breast-conserving surgery and intraoperative radiotherapy (IORT), based on the hypothesis that re-irradiation to a limited volume will be effective with an acceptable occurrence of side effects including fibrosis.**

## 4-Objectives

### 4.1. Primary objective

To evaluate the tolerance of IORT delivered during a second breast- conserving surgery

### 4.2. Secondary objectives:

To evaluate the effect of IORT on:

- Cosmetic results,
- Early Toxicities :
  - o Hematoma
  - o Lymphorrhoea (punctures > 2).
  - o Breast infection
  - o Erythema.
- Late Toxicities
  - o Telangiectasia.
  - o Breast Pain
  - o Skin hyperpigmentation
  - o Skin ulceration
  - o Cutaneous atrophy
- Quality of life according to EORTC QLQ-C30 and BR23
- Survival including:
  - o Local relapse-free survival
  - o Metastasis relapse-free survival
  - o Disease-free survival
  - o Overall survival
  - o Mastectomy-free interval,

#### 4.3. Ancillary objectives:

To prospectively identify, through a protein assay (blood sample) the individual risk of patients to develop severe late toxicity.

To prospectively identify, through a rapid genomic assay (effusion samples) the impact of the dose of radiation administered to the patient's tissue by identifying the molecular processes involved in the individual's response.

The correlation between the proteomic data and the fibrosis rate will be also evaluated according to ancillary studies.

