
ANCILLARY STUDY	
To prospectively identify patients with a personal intrinsic radiosensitivity, through a protein and genomic assay:
 
 
 The proteomic approach (mandatory) will score the inherent individual risk of radiation-induced severe late effects and intrinsic radiosensitivity by dosage of proteins identified in the "radiosensitivity" program.
 
 The genomic approach (optional) will evaluate the genomic acute changes on tumor bed after delivery of a single dose of 20 Gy.
 
												
TREATMENT	
Surgery :
 
Tumorectomy will be performed according to the current standards, obtaining "clear" margins.
 
The axillary lymph node control will depend on the initial management (clinical and ultrasound) of these N0 patients, chosen by the teams.
 
Intra Operative Radiotherapy (IORT): After the excision of the tumor, IORT will be delivered. A single dose of 20 Gy by 50 kV photons (Intrabeam™) will be administered in tumor bed. The addition of IORT does not modify the surgical procedure.
												

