### **7.2.2. Modalities of IORT:**

Prior to the insertion of the adequate applicator in the surgical cavity, the surgeon cautiously checks the hemostasis, the perfect vicinity (absence of blood or serum) of the excision cavity. The presence of blood or serum would seriously reduce the dose received by the surrounding mammary gland in this situation of important steep dose fall-off.

The diameter of the applicator, varying from 25 to 50 mm, is chosen under visual control, by the surgeon and the radiation oncologist, in order to be perfectly adapted to the size of the cavity left by the removal of the tumor. Thanks to its spherical shape, the applicator is easily covered by the gland and does not require extensive tissue mobilization, which is a source of late fat necrosis.

The cavity tissue will then be approximated around the spherical applicator with one or two purse string sutures with a harmonious thickness of mammary gland

The suture is then tightened. Sterile gauzes or two Beckmann orthostatic spacers are added to obtain adequate skin spacing between the applicator and the skin, defined as  $\geq 1$  cm, to avoid skin toxicity.

The course of the irradiation is monitored by the radiation oncologist and the medical physicist. A unique dose of 20 Gy is prescribed at the applicator surface and the time of irradiation depends on its diameter with a median of about 30 minutes (ranging from 18 to 40 minutes). The exact length of the radiation time is determined by the applicator size (ranging from 20 to 40 minutes) and the additional time for the entire IORT procedure will be around 40 to 60 minutes. Then, the surgeon removes the applicator. Surgical clips are placed in the tumor bed to facilitate further imaging follow-up. The cavity is closed and remodelled. A post-operative drainage could be necessary.

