## 16- GENOMIC and IORT (Optional)

---

The miRNA expression profiles are altered in a specific and radiation dose-dependent manner (an mRNA radiation exposure "signature") that provides a sensitive and effective, biodosimetry test.

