## 16.1. Serum collection from resected cavity (Investigation centers, France):

In all investigation centers involved in the genomic assay, 5 ml of operative cavity serum will be collected from each patient before IORT and 5 ml after the IORT (one single dose of 21 Gy IORT). Five volumes of RNAProtect Cell Reagent (Qiagen) will be mixed with one volume of serum and immediately stored at -80C until shipping to the ICM. Samples will be regrouped at the ICM and send to the University of Arizona.

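### The optional genomic sub-study cannot separate the effect of irradiation on cavity-fluid miRNA from that of surgery and elapsed time, because every patient is irradiated and there is no unirradiated comparator

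*Protocol*

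**What the plan says.** The aim appears in two forms. Section 4.3 asks the genomic assay to identify "the impact of the dose of radiation administered to the" patient's tissue, by way of the molecular processes behind each patient's response. The synopsis is narrower: the genomic approach "will evaluate the genomic acute changes on tumor bed after delivery of a single dose of 20 Gy".

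Sections 3.2 and 16.3 both describe the miRNA changes to be looked for as a response to irradiation. Section 16 opens by stating that miRNA profiles are "altered in a specific and radiation dose-dependent manner" and that this supports a biodosimetry test. Section 16.4 carries the miRNAs selected in 16.3 into a customised CLPA panel.

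Sampling is set in section 16.1: "5 ml of operative cavity serum will be collected from each patient before IORT and 5 ml after the IORT". Section 6 describes a single-arm trial, and section 7.2.2 fixes one dose: "A unique dose of 20 Gy is prescribed at the applicator surface". The same section says the "additional time for the entire IORT procedure will be around 40 to 60 minutes".

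**The concern.** A before/after comparison supports a statement about radiation only if the fluid would have stayed the same without radiation, or if a comparator shows how much it would have changed. Neither condition is met. Between the two samples the wound has been open longer, and the gland has been sutured around an applicator. Section 7.2.2 also has the surgeon check that the cavity is free of blood and serum before the applicator goes in. The later fluid may therefore have collected largely after the first sample was taken. That last step is an inference, since the sections shown do not state the exact sampling moments.

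The protocol applies the missing principle in its other ancillary study: section 15.2 pairs each irradiated lymphocyte culture with a sham-irradiated 0 Gy control. The genomic study has no counterpart.

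What is at stake is the label on the result. miRNAs that move because of surgery or time could be carried into the panel as a radiation signature, and a reader of sections 4.3 and 16 could take them as evidence of dose dependence.

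**Working it through.** The protocol gives no sample size or power for this sub-study, so there is no figure to reproduce. The check is whether the effects of interest can be estimated at all.

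**Inputs**
- Patients: 65 planned (synopsis, section 6). This is an upper limit, because genomic sampling is optional.
- Samples: one before and one after IORT per patient (16.1).
- Irradiated: every patient (single arm, section 6).
- Prescribed dose: one level, coded here as 20 Gy (7.2.2).

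**Model.** For one miRNA in patient *i*, let *t* = 0 before and *t* = 1 after IORT:

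Y(i,t) = patient(i) + T·t + R·irradiated(i,t) + B·dose(i,t) + error

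T is the effect of surgery and elapsed time, R the effect of irradiation, and B the change per Gy. Under the protocol, irradiated(i,t) = t and dose(i,t) = 20t for every patient.

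**What can be estimated.** The within-patient difference is

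Y(i,1) − Y(i,0) = T + R + 20B + error

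Every patient contributes the same sum, so only the sum can be estimated.

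**Rank**
- Rows: 65 × 2 = 130.
- Columns: 65 patient effects + 3 = 68.
- Rank: 65 + 1 = 66.
- Deficiency: 68 − 66 = 2. The correlation between the after and irradiated indicators is 1.00, and dose is an exact multiple of both.

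For any number of patients *n* there are *n* + 3 columns and the rank is *n* + 1, so recruiting more patients does not help. Coding the dose as 21 instead of 20 changes nothing, because it is still one constant.

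**What a comparator would change (illustration).** Add before/after pairs of unirradiated cavity fluid from 10 further patients; 10 is an assumption, and one pair would give the same conclusion.
- Rows: 130 + 20 = 150.
- Columns: 68 + 10 = 78.
- Rank: 77.

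Irradiation now separates from surgery and time. One deficiency remains: dose still cannot be separated from irradiated yes/no, which would need at least two different non-zero dose values.

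**Would recorded covariates rescue it?** Applicator diameter varies from 25 to 50 mm, but section 7.2.2 matches it to the cavity. Irradiation time is determined by applicator size and forms part of the sampling interval. These variables are tied to each other and to the wound, and none supplies an unirradiated sample. They can describe the data but cannot restore attribution.

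**Stated dose.** The synopsis and section 7.2.2 give 20 Gy; section 16.1 gives 21 Gy for the same procedure.

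**The case against.** The strongest reply is that no dose-response analysis is planned. Section 4.3 can be read as the impact of the one dose given, seen through the molecular processes in each patient, and the synopsis wording supports that. The opening sentence of section 16 is a premise, not a result this trial promises. This stands. A reader might infer that the sub-study sets out to estimate a dose slope and fails; the documents do not show that. What survives is narrower: the data cannot show dose dependence, and the text should not leave the impression that they can.

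A second reply is that the work is optional and exploratory. Section 16.3 is a screen, the panel in 16.4 serves to validate the assay chemistry, and the point-of-care system is a future possibility. No endpoint or stopping rule uses the result. This also stands, and it keeps the point minor. It does not answer the attribution problem, because sections 3.2 and 16.3 call the change a response to radiation.

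Third, Appendix 6 is a genomic sampling procedure that is listed but not shown, and it may already record sampling times. Their absence therefore cannot be asserted.

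Leaving the matter to a statistical analysis plan would not resolve it, since no analysis can supply a control sample that was not collected.

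**Conclusion.** The point holds in a limited form. As sections 3.2, 6 and 16 describe the design, the sub-study estimates one quantity per miRNA: the total before-to-after change. The part due to radiation cannot be separated from surgical-wound and time effects over a procedure that adds about 40 to 60 minutes, and dose dependence cannot be shown at any sample size.

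The size of the bias cannot be given. It is tempting to say that radiation's share lies somewhere between 0 and 100% of the change, but that is not a valid bound. If T and the radiation part have opposite signs, the share falls below 0 or exceeds 100%. Nor do the documents show that the changes are not due to radiation; they show only that this trial cannot tell.

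The 20 Gy and 21 Gy figures are a discrepancy in the text. They should not be read as two dose levels from which a slope could be learned.

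The conclusion assumes that no unirradiated or time-matched cavity sample is specified in the appendix not shown. It concerns an optional ancillary study and does not touch the primary endpoint.

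**What to change.** - Reword sections 3.2, 4.3, 16.3 and 16.4 as an exploratory description of within-patient before/after change in cavity-fluid miRNA, in line with the synopsis, which speaks only of acute changes.
- State in 16.4 that miRNAs chosen for the panel are candidates whose change this trial cannot attribute to radiation or to dose, and that they need confirmation against unirradiated controls.
- Mark the dose-dependence sentence at the start of section 16 as a premise that this trial does not test.
- Record the time of both samples, if the sampling procedure does not already do so, and use the times for description only.
- Reconcile the dose stated in section 16.1 with the synopsis and section 7.2.2.

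The cost is a few sentences and, at most, two times on the sampling form. No patients, samples or procedures are added. The downside is a more modest claim for an optional sub-study.
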